4.5.2. Patient level

Compliance will be described by patients using the following criterion:

- Total patient compliance: A patient is compliant if all courses of the patient are compliant.

Non-compliant courses and infusions will be listed by patient showing all of the above criteria. The criterion leading to non-compliance will be flagged.

4.6. Efficacy Analyses

The efficacy analyses will be performed on the FAS. The analyses of the primary endpoint will be repeated on the PPS as sensitivity analysis (only if the PPS is different from the FAS). All efficacy endpoints will be analyzed overall and by subgroups of relapsing Ig-pretreated patients and Ig-naïve patients. Endpoints will also be listed by patient status (Ig-naïve/Ig-pretreated).

If a patient is treated with a non-allowed treatment during the study period, then all efficacy variables measured after the intake of these non-allowed treatments will be censored for the efficacy analyses. Assessments of primary and secondary criteria after a forbidden treatment will be flagged in all listings.

The following treatments are not allowed during the study:

- Any other investigational product administered within the last month prior to screening
- Plasma exchange, blood products or derivatives other than the study drug.
- Immunomodulatory or immunosuppressant agents (e.g. including but not limited to cyclophosphamide, cyclosporine, interferon- α , interferon- β 1a, anti-CD20, alemtuzumab, aziathioprine, etanercept, mycophenolate mofetil, methotrexate) and hemotopoeitic stem cell transplantation.
- Oral or systemic corticosteroids therapy if administered with an increasing dosage or introduced at a dose higher than 10 mg daily prednisolone or equivalent. Topical corticosteroids are allowed.

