1.1.2. Treatment of CIDP and course of the disease

The spontaneous evolution of the disease in the absence of any therapy has not been well described in the literature. The effectiveness of treatment with corticosteroids was shown when chronic polyradiculoneuropathy was first described by Austin in 1958 [8].

Three therapeutic options have proved to be efficacious in CIDP: IVIg, oral corticosteroids and plasma exchange. The EFNS/PNS guideline recommends the use of IVIg or corticosteroids as first line treatment. Plasma exchange, which is less widely available and less tolerated, is only recommended as an alternative in case IVIg and corticosteroids are inadequate. The American Academy of Neurology considers that IVIg should be offered for the long-term treatment of CIDP (Level A recommendation) [9].

Regarding IVIg, a meta-analysis in a Cochrane review of 5 double blind placebo-controlled randomised trials showed that a significantly higher proportion of patients improved in disability within one month after IVIg treatment compared with placebo [10]. Only one study (ICE study) had a long-term follow-up; in this study, 57 responder patients were re-randomised for an extension 24 - week phase between either IVIg at 1 g/kg or placebo every 3 weeks. The percentage of relapse was 13% with the IVIg and 45% with the placebo (p=0.011) [11].

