5.4. Discontinuation criteria / Stopping rule(s)

All patients are free to withdraw from participation in this study at any time, for any reason, and without prejudice. The Investigator must withdraw from the study any patient who requests to stop participating in the study. Patients who withdraw their consent will be asked to undergo the study assessments scheduled at the EOS visit. They will be advised that participation to the EOS visit is voluntary but is their best interest.

The Investigator must discontinue study drug administration to a patient and perform an EOS visit at the request of the Sponsor or if the patient:

- Experiences an AE - including an AE due to a clinically significant laboratory abnormality - that justifies study drug premature discontinuation.

Undergoes protocol deviation that could endanger the patient safety.

- Becomes pregnant.

Moreover, the Investigator may discontinue a patient from study drug administration if:

- Either the patient's adjusted INCAT disability score increases by 1 point, compared to baseline,

AND

Judging on the clinical examination and/or the neurological scales assessments, the Investigator considers change in patient's treatment (such as, administration of another IVIg, increase or initiation of a corticotherapy, immunosuppressive therapy, plasma exchange) is mandatory. Clinical examination findings as well as neurological scales assessments will have to be reported on the EOS visit as appropriate;

- Or the patient's adjusted INCAT disability score increases by at least 2 points compared to baseline.

If a patient is prematurely discontinued, the date and reason of discontinuation will be documented in the eCRF.

If a patient is withdrawn because of an AE, he/she will be followed up until complete resolution or stabilisation of the AE.

Patients lost to follow-up will be considered as discontinued from the study. A patient will be considered as lost to follow-up only after having exhausted all means of contact. Investigators must make every effort to contact the patient and/or his/her family or relatives to obtain the maximum of the per protocol requested information. All contact attempts will be documented in the patient's medical records.

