7.2. Concomitant Medication

The term ‘concomitant medication’ refers to any medication that the patient receives at any time during the study, i.e. from screening to EOS visit. This includes the screening/baseline period,

treatment period and follow-up as defined in the protocol. At each visit, the Investigator will ask the patient about any medication taken since the last visit. All concomitant medication must be recorded in the patient’s medical file and documented on the appropriate pages of the eCRF.

Treatments not allowed during the study are the following:

- Plasma exchange, blood products or derivatives other than the study drug.

- Immunomodulators/immunosuppressors agents (e.g. including but not limited to cyclophosphamide, cyclosporine, interferon- α , interferon- β 1a, anti-CD20, alemtuzumab, aziathioprine, etanercept, mycophenolate mofetil, methotrexate) and haematopoietic stem cell transplantation.
- Introduction or increasing dose of systemic corticosteroids therapy, and/or systemic corticosteroids therapy at a dose higher than 10 mg prednisolone per day, or equivalent. Topical corticosteroids are permitted.
- Loop diuretics administered during the last 24 hours before IVIg infusion planned date. In this case, the study drug infusion date will have to be postponed.

Routine pre-medication (to prevent known drug related adverse reaction) are not recommended to avoid masking potential AEs. However, patients who have routinely been receiving pre-medication with previous Ig treatments may continue to receive the same pre-medication.

Other medications which are necessary for the patient's welfare or well-being may be given at the discretion of the Investigator.

All concomitant medications must be recorded in the patient's medical records and documented on the appropriate pages of the eCRF.

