12.9.1. Primary Efficacy Variable(s)

12.9.1. 1. Description of the primary efficacy variable(s)

The primary efficacy endpoint will be the responder rate at EOS visit.

Responder patients are defined as patients with a decrease of at least 1 point in the adjusted INCAT disability score between baseline and the EOS visit.

If a patient is treated with a not-allowed treatment during the study period, then all efficacy variables measured after the intake of these not-allowed treatments will be censored for the efficacy analyses.

12.9.1. 2. Hypothesis Test and Primary Analysis Model

The responder rate will be tested against the historical responder rate of 33.3% with a one-sided Clopper-Pearson test (exact binomial test) at the nominal level of significance of 2.5%.

The null and alternative hypotheses are as follows:

$$H_0: \pi_{(110E)} \leq 33.3\%$$

$$H_a: \pi_{(110E)} > 33.3\%$$

The proportion of responders and the associated 95% confidence interval will be estimated using a Clopper-Pearson method. The primary analysis will be performed on the FAS.

12.9.1. 3. Handling of Missing Data

The primary analysis of the primary criterion will be done using the baseline and last available assessment of the adjusted INCAT disability score after the first study drug administration. If the score at EOS visit is missing, then the Last Observation Carried Forward (LOCF) approach will be applied and the last available adjusted INCAT disability score will replace the missing value at EOS visit. Other imputation methods might be defined in the SAP for the purpose of sensitivity analyses.

12.9.1. 4. Prognostic factors and covariates

No prognostic factors will be used in the statistical model.

12.9.1. 5. Other analyses for the primary variable

The analysis of the primary criterion will be repeated on the PPS as sensitivity analyse.

Other sensitivity analyses might be defined in the SAP.

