12.9.2. Secondary efficacy variables

12.9.2. 1. Description of secondary efficacy variables

- Responder rate at 12 weeks.
- Time to response.
- Percentage of patients at 12 weeks and EOS visit with no change in CIDP treatment.
- Changes from baseline to 12 weeks and EOS visit in the following scores:
 - Adjusted INCAT disability score;
 - Grip strength with the Martin vigorimeter in both hands;
 - Rasch-built Overall Disability Scale (R-ODS);
 - Patient and Investigator Clinical Global Impression (CGI);
 - Medical Research Council (MRC) 12 muscles sum score (0 to 5) and Rasch-modified MRC (0 to 3).

12.9.2. 2. Analysis of secondary efficacy variables

All parameters as well as the change from baseline will be summarised using Hodges-Lehmann point estimates and corresponding confidence intervals. Time to response will be analysed using a Kaplan-Meier method.

If a patient is treated with a not-allowed treatment during the study period (Plasma exchange, blood products or derivatives other than the study drug, immunomodulatory/immunosuppressant agents, corticotherapy, if administered with an increasing dosage or introduced orally or systematically at a dose higher than 10 mg daily prednisolone or equivalent), then all adjusted INCAT disability scores measured after the intake of these not-allowed treatments will be censored for the efficacy analyses.

A LOCF approach will be used to handle the missing data of secondary endpoints. All details to handling of missing data will be provided in the SAP.

The 12-week and the EOS visit values will be compared to the baseline value using appropriate statistical tests. A significance level of 5% (two-sided) will be applied.

The adjusted INCAT disability score will additionally be presented graphically over the patients' follow-up during the study.

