3.5.2. Protocol deviations

The protocol deviations and corresponding categories are defined in the protocol deviation plan as well as their consequence for the inclusion in the different analysis sets. The following protocol deviations categories will be studied:

- Deviations regarding inclusion criteria
- Deviations regarding exclusion criteria
- Deviations regarding the study drug
- Deviations regarding safety assessments
- Deviations regarding assessment of laboratory parameters (including biomarkers)
- Deviations regarding visit windows
- Deviations regarding informed consent
- Deviations regarding forbidden treatments during the study
- Deviations regarding overdose/misuse of study drug
- Other protocol deviations
- Deviations regarding the primary efficacy endpoint
- Deviations regarding other efficacy endpoints
- Deviations regarding exploratory endpoints

- Deviations regarding the ancillary study

All the protocol deviations which occurred during the study will be examined during the final data review meeting. All adjudicated protocol deviations will be presented in data listings.

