4.6.1. Primary efficacy endpoint

The primary efficacy criterion is the response rate of the patients at EOS visit. Response is defined as a patient with a decrease of at least 1 point between baseline and the EOS visit in the adjusted INCAT disability score.

The primary analysis of the primary efficacy criterion will be done using the baseline and last available assessment of the adjusted INCAT disability score after the first study drug administration. That is, if the score at EOS visit is missing, then the Last Observation Carried Forward (LOCF) approach will be applied and the last available adjusted INCAT disability score will replace the missing value at EOS visit.

Similarly, if the assessment of the adjusted INCAT disability score is censored due to an intake of a forbidden treatment, the adjusted INCAT disability score from the last assessment before the intake of the forbidden treatment is used as replacement for the assessment of the EOS visit.

The response rate at the EOS visit will be tested against the historical response rate of 33.3% with a one-sided Clopper-Pearson test (exact binomial test ([Clopper 1934](#))) at the nominal level of significance of $\alpha=2.5\%$ for the overall set of patients, one-sided Clopper-Pearson test will not be performed by subgroup.

The null and alternative hypotheses are as follows:

$$H^0: \pi_{I10E} \leq 33.3\%$$

$$H^1: \pi_{I10E} > 33.3\%$$

The number and percentage of responders at EOS will be presented with descriptive statistics. The associated exact 95% Clopper-Pearson confidence interval will be calculated for the proportion of responders. A table will be produced for the subgroup of patients with response at EOS visit presenting the earliest visit at which response was achieved.

The primary analysis will be performed using the FAS and a sensitivity analysis will be performed using the PPS.

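### A new corticosteroid course at or below 10 mg/day is forbidden on study but missing from the censoring list, so the post-steroid score stays in the primary test

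*SAP*

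**What the plan says.** Protocol 7.2 lists what may not be given during the study. Its corticosteroid item is: "Introduction or increasing dose of systemic corticosteroids therapy, and/or systemic corticosteroids therapy at a dose higher than 10 mg prednisolone per day". Starting, increasing, and exceeding 10 mg/day are three separate conditions, and starting carries no dose limit. Protocol 7.1 and exclusion criterion 17 use the same three conditions for the period before screening.

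For the primary endpoint, Protocol 12.9.1.1 says that after a not-allowed treatment "all efficacy variables measured after the intake of these not-allowed treatments will be censored for the efficacy analyses". It gives no list of treatments. The one list in the protocol's statistics section is in 12.9.2.2, where corticotherapy counts "if administered with an increasing dosage or introduced orally or systematically at a dose higher than 10 mg daily prednisolone or equivalent". SAP 4.6 states the censoring rule for all efficacy variables and places its own list directly beneath it. The corticosteroid item there reads: "Oral or systemic corticosteroids therapy if administered with an increasing dosage or introduced at a dose higher than 10 mg daily prednisolone or equivalent".

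SAP 4.6.1 carries the censoring into the primary test. When a score is censored, the adjusted INCAT score from "the last assessment before the intake of the forbidden treatment is used as replacement for the assessment of the EOS visit".

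**The concern.** In both analysis lists the 10 mg limit is attached to the word for starting treatment. One case falls through: a patient who newly starts a flat dose at or below 10 mg/day and continues I10E. Protocol 7.2 does not allow that treatment, yet under the SAP 4.6 list the later scores are not censored and the return to the last pre-steroid score is not triggered.

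The protocol itself regards steroids as active in this disease: "Three therapeutic options have proved to be efficacious in CIDP: IVIg, oral corticosteroids and plasma exchange". With no control arm, an improvement that follows an added steroid cannot be separated from the effect of I10E. It enters the responder count that is compared with a fixed 33.3%, so the error favours I10E.

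**Working it through.** **Texts side by side**

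| Event on study | Protocol 7.2 | Protocol 12.9.2.2 and SAP 4.6 lists |
|---|---|---|
| Dose increase | not allowed | censored |
| New start above 10 mg/day | not allowed | censored |
| New start, flat, at or below 10 mg/day | not allowed | **not listed** |

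One could read a move from zero to 10 mg as an increasing dosage. But both lists name starting separately and give it its own dose limit, and that limit would have no function if every start were an increase. The SAP's section on changes from the protocol (4.10) does not mention the point.

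**Do other rules close the gap for a patient who stays on I10E?**

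- Protocol 5.4 lets a worsening patient be stopped, but it is optional: "the Investigator may discontinue a patient from study drug administration if".
- Protocol 3.1.5 and 8.2.7 place the EOS visit before any other CIDP treatment in early discontinuation or withdrawal. They do not reach a patient who continues.
- SAP 3.2 counts withdrawal for lack of efficacy as non-response. This applies only if the patient is withdrawn.
- The PPS repeat drops the patient only if the deviation is graded major. SAP 3.5.2 leaves this to another document: "The protocol deviations and corresponding categories are defined in the protocol deviation plan".

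**Size**

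Inputs: null rate 0.333, planned rate 0.60, one-sided 2.5%, 38 evaluable patients, 42 enrolled (Protocol 12.3 and 12.9.1.2; SAP 2.3). Write T(n, r) for P(X ≥ r), with X binomial(n, 0.333).

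The plan's own figure first. At n = 38 the smallest r with T(38, r) ≤ 0.025 is 19: T(38, 19) = 0.0244, and power at 0.60 is 0.922. At n = 37 the critical value is also 19 and power is 0.892. So 38 is the smallest n that reaches 90% power, as stated. One patient decides the result at the boundary, since T(38, 18) = 0.0502. At n = 42 the critical value is 21 and T(42, 21) = 0.0185.

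The number k of affected patients is an assumption.

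*Upper bound.* If k patients always count as responders, the other n − k must supply r − k responders, so the error is T(n − k, r − k).

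| k | n = 38, r = 19 | n = 42, r = 21 |
|---|---|---|
| 0 | T(38, 19) = 0.0244 | T(42, 21) = 0.0185 |
| 1 | T(37, 18) = 0.0380 | T(41, 20) = 0.0287 |
| 2 | T(36, 17) = 0.0579 | T(40, 19) = 0.0437 |

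*Milder case.* Let each affected patient respond with probability 0.6 (illustrative; it equals the planned I10E rate).

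- k = 1: 0.6·T(n − 1, r − 1) + 0.4·T(n − 1, r).
  - n = 38: 0.6 × 0.0380 + 0.4 × 0.0176 = 0.0298.
  - n = 42: 0.6 × 0.0287 + 0.4 × 0.0134 = 0.0225 (from unrounded terms).
- k = 2: 0.36·T(n − 2, r − 2) + 0.48·T(n − 2, r − 1) + 0.16·T(n − 2, r).
  - n = 38: 0.36 × 0.0579 + 0.48 × 0.0281 + 0.16 × 0.0124 = 0.0363.
  - n = 42: 0.36 × 0.0437 + 0.48 × 0.0212 + 0.16 × 0.0094 = 0.0274.

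Closing the gap changes none of n, alpha or the critical value. It changes only which score is used for the affected patients.

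**The case against.** The strongest reply is that the protocol's primary rule is already right. Section 12.9.1.1 censors after any not-allowed treatment, 7.2 defines what is not allowed on study, and SAP 3.5.1 repeats the rule without a list. On this view the fault is a drafting slip in one SAP item. It stands to this extent: correcting SAP 4.6 is enough for the primary test. It does not clear the protocol, because 12.9.2.2 applies the same narrow list to all adjusted INCAT scores in the efficacy analyses. A programmer working from SAP 4.6 would apply the list printed there.

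Second, the case is narrow. The patient must start a low dose against protocol, stay on I10E, be a non-responder before the steroid and become a responder after it. That is fair, and nothing in the documents shows how often it would happen.

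Third, it would be seen before lock. SAP 4.6.2 has the study physician review steroid use, and deviations go to the data review meeting. But that physician's flag uses a threshold above 10 mg/day for more than 10 days and serves a different endpoint. Neither step changes the FAS result.

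Fourth, the protocol does not say that 10 mg/day or less is effective, and it allows stable background doses up to that level. True, but it still forbids any new start, and no document justifies a looser rule for the analysis.

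Fifth, 33.3% is a conservative benchmark, the upper confidence limit of an observed 12/58 = 20.7%. At a true rate of 20.7% the 19-of-38 rule has an error of about 0.006%, and still only about 0.01% or 0.03% with one or two fixed responders. This softens the practical risk. The nominal error at the stated null still rises as shown.

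**Conclusion.** The concern holds. SAP 4.6 and Protocol 12.9.2.2 omit a treatment that Protocol 7.2 forbids, the omission reaches the primary test through SAP 4.6.1, and it is undeclared. With one or two affected patients, the one-sided error at the 33.3% null is at most 3.8% or 5.8% at n = 38, and 2.9% or 4.4% at n = 42. In the milder case it is 3.0% or 3.6%, and 2.3% or 2.7%; a single affected patient at n = 42 then stays below 2.5%. These figures rest on an assumed number of patients and assumed response probabilities. Some of these patients would be responders on their pre-steroid score anyway, so the true effect may be smaller. The point should be corrected because it concerns the only confirmatory test and the remedy is cheap, not because a large bias has been shown.

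**What to change.** Reword the corticosteroid item in SAP 4.6 to match Protocol 7.2: a start at any dose, any dose increase, or any dose above 10 mg/day prednisolone or equivalent. Later scores are then censored and the last pre-steroid score is used. Align Protocol 12.9.2.2 for consistency; the primary test does not depend on that edit.

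If the 10 mg limit on new starts is intended, declare it in SAP 4.10 and rerun the primary test under the 7.2 definition as a sensitivity analysis.

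As a tidy-up, remove the item on investigational products taken before screening from the SAP 4.6 list, which is meant to cover treatments during the study. The separate definition of a change in CIDP treatment in SAP 4.6.2, item 3, can stay as it is.

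Cost: one line of SAP wording, or one extra table if the threshold is kept. The responder rate may fall slightly.

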4.6.1. Primary efficacy endpoint

The primary efficacy criterion is the response rate of the patients at EOS visit. Response is defined as a patient with a decrease of at least 1 point between baseline and the EOS visit in the adjusted INCAT disability score.

The primary analysis of the primary efficacy criterion will be done using the baseline and last available assessment of the adjusted INCAT disability score after the first study drug administration. That is, if the score at EOS visit is missing, then the Last Observation Carried Forward (LOCF) approach will be applied and the last available adjusted INCAT disability score will replace the missing value at EOS visit.

Similarly, if the assessment of the adjusted INCAT disability score is censored due to an intake of a forbidden treatment, the adjusted INCAT disability score from the last assessment before the intake of the forbidden treatment is used as replacement for the assessment of the EOS visit.

The response rate at the EOS visit will be tested against the historical response rate of 33.3% with a one-sided Clopper-Pearson test (exact binomial test ([Clopper 1934](#))) at the nominal level of significance of $\alpha=2.5\%$ for the overall set of patients, one-sided Clopper-Pearson test will not be performed by subgroup.

The null and alternative hypotheses are as follows:

$$H^0: \pi_{I10E} \leq 33.3\%$$

$$H^1: \pi_{I10E} > 33.3\%$$

The number and percentage of responders at EOS will be presented with descriptive statistics. The associated exact 95% Clopper-Pearson confidence interval will be calculated for the proportion of responders. A table will be produced for the subgroup of patients with response at EOS visit presenting the earliest visit at which response was achieved.

The primary analysis will be performed using the FAS and a sensitivity analysis will be performed using the PPS.

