3.2. Handling of Missing Data and Outliers

Regarding the primary criterion, a patient will be also considered as a non-responder if the patient is withdrawn due to lack of efficacy of the treatment (insufficient response to the investigational medicinal product [IMP]). In all other cases, if the INCAT score at EOS visit is missing, then the Last Observation Carried Forward (LOCF) approach will be applied and the last available adjusted INCAT disability score will replace the missing value at EOS visit.

The LOCF approach will also be used to handle the missing data of the secondary endpoint for adjusted INCAT and response at week 12 only.

When AEs are documented in the diary, dates of AE onset may be missing and as a result, TAAE cannot be defined. For AEs with a missing or incomplete start date, the response to the question “Did the AE start within 72 hours of an infusion” will be used for determining if the AE is temporally related to the infusion.

Partial dates of first symptoms and partial dates of diagnosis will be imputed by 15 if only the day is unknown and by 1st July if day and month are unknown. No imputation will be done if the year is unknown.

For the calculation of duration of AEs, partial start and end dates will be imputed with the first and last possible date within the period defined by the partial date, respectively. In general, no

calculation of duration will be made if either the start date or stop date is missing, i.e., cannot be imputed using pre-determined rules. No other general rules for the replacement of missing data are planned.

Data listings will always show the original CRF reported values and not the imputed values.

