4. STATISTICAL ANALYSIS

4.1. Disposition of Patients

In order to describe population, descriptive statistics (number, or number and percentages) as well as a listing will be provided for the following patients:

- Patients screened (patients who signed informed consent)
- Patients enrolled
- Patients with a screening failure
- Patients who were re-screened
- Patients who received study treatment (TTS)
 - Patients participating in the ancillary study
 - Patients who completed the study
 - Patients withdrawn early from the study and reasons for study discontinuation [Adverse event (AE), Protocol deviation, Withdrawal of consent, Lost to follow-up, Insufficient response to IMP, Other]
 - Patients withdrawn early due to insufficient response of IMP with reason for insufficient response (INCAT, MRC sum score, R-ODS, Grip strength, CGI-Patient, CGI-Investigator, Clinical examination, Premature termination of IMP) and follow-up treatment (IVIg, Corticosteroids, Immunomodulatory or immunosuppressive agent or Other)
- Patients included in the FAS
- Patients included in the PPS

Percentages for patients enrolled, failed screening or re-screened will be calculated using the number of unique patients screened as the denominator. For the TTS, percentages will be calculated using the number of patients enrolled as the denominator, any other populations will use number of patients within the TTS as the denominator. For screen failure patients, a listing will be produced with the reason for screening failure and the specifications provided by the investigator. For patients who discontinued the study, a listing will be produced with the reasons of study discontinuation and the specifications provided by the investigator. Listings will also be produced for study entry, end of study (EOS) and patient study visits.

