4.10.1. Efficacy

Planned analysis associated with the ultrasonography ancillary study will not be performed due to non-collection of required data.

The protocol (section 12.9.2.2) states for secondary efficacy data that “A LOCF approach will be used to handle the missing data of secondary endpoints. All details to handling of missing data will be provided in the SAP”. However LOCF approach will only be used for criteria using adjusted-INCAT.

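### SAP 4.6.1 omits the SAP 3.2 rule that withdrawal for lack of efficacy is non-response, and no planned responder analysis covers all treated patients

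*SAP*

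**What the plan says.** The primary endpoint is a fall of at least 1 point in adjusted INCAT from baseline to the EOS visit. It is tested once, one-sided at 2.5%, against 33.3%.

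- **SAP 3.2**, on the primary criterion: "a patient will be also considered as a non-responder if the patient is withdrawn due to lack of efficacy of the treatment". It then continues "In all other cases, if the INCAT score at EOS visit is missing", LOCF applies.
- **SAP 4.6.1**, which specifies the primary analysis: "primary analysis of the primary efficacy criterion will be done using the baseline and last available assessment of the adjusted INCAT disability score" after first dosing, with LOCF if the EOS score is missing. It has no exception for lack of efficacy and no reference to 3.2. After a forbidden treatment, "the adjusted INCAT disability score from the last assessment before the intake of the forbidden treatment is used as replacement" for the EOS score.
- **Protocol 12.9.1.3**: if the EOS score is missing, "the last available adjusted INCAT disability score will replace the missing value at EOS visit", again with no exception. Protocol 12.9.1.1 adds that after a forbidden treatment "all efficacy variables measured after the intake of these not-allowed treatments will be censored for the efficacy analyses".
- **SAP 4.10.1**, efficacy changes from the protocol: on missing data it lists only the narrower use of LOCF for secondary endpoints, "However LOCF approach will only be used for criteria using adjusted-INCAT".
- **SAP 4.1** tabulates withdrawals for insufficient response "with reason for insufficient response (INCAT, MRC sum score, R-ODS, Grip strength, CGI-Patient, CGI-Investigator, Clinical examination, Premature termination of IMP").
- **Analysis sets (SAP 3.5.1, 4.6)**: the FAS is treated patients with an available primary assessment. The PPS is a subset of the FAS. Repeating the primary analysis on the PPS, if it differs from the FAS, is the only sensitivity analysis. Protocol 12.9.1.3 and 12.9.1.5 left room for others in the SAP, and the SAP defines none.

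**The concern.** In a single-arm, open-label trial with one test against a fixed rate, the result rests on one count of responders. That count should not depend on which SAP section the programmer has open. Someone working from 4.6.1 alone would count as a responder a patient withdrawn for insufficient response on, say, grip strength or CGI whose last adjusted INCAT is still a point better than baseline. Someone working from 3.2 would not. The SAP also does not say which rule comes first when such a patient has taken a forbidden treatment as well.

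The second part concerns the denominator. A treated patient with no post-dose score leaves the FAS and therefore the PPS, so no planned responder analysis shows what happens if that patient is counted as a failure.

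**Working it through.** **Plan's own figure.** Inputs from SAP 2.3 and protocol 12.3: p0=0.333, p1=0.60, one-sided α=0.025, n=38. The critical value is the smallest r with P(Bin(38, 0.333) ≥ r) ≤ 0.025.

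- r=18: p=0.0502, fails.
- r=19: p=0.0244, passes.
- Power: P(Bin(38, 0.60) ≥ 19) = 0.9216. At n=37 it is 0.892, so 38 is the smallest size reaching 90% and the plan's figure reproduces.

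**Who is classified differently.** Two conditions must both hold: withdrawal for insufficient response, and a last or early-EOS adjusted INCAT at least 1 point below baseline.

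- Protocol 5.4 ties efficacy-based discontinuation to adjusted INCAT worsening: a 1-point rise over baseline together with a judgement that a treatment change is mandatory, or a rise of at least 2 points. A patient discontinued on these criteria is worse than baseline and is normally a non-responder under either rule.
- Protocol 3.1.5 has the early EOS visit within 7 days and before other CIDP treatment, so a score will often exist.
- SAP 4.1 allows withdrawal for insufficient response on grounds other than INCAT, so the disputed patient is possible.

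**Effect of one disputed patient.** One reclassified responder changes the verdict only when the count is exactly 19.

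**Illustration, not an estimate.** The documents give no rate of such cases. Suppose exactly m of 38 are responders under 4.6.1 and not under 3.2, with X ~ Bin(38−m, p) among the others. The verdicts differ when 19−m ≤ X ≤ 18.

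| m | p=0.60 | p=0.50 |
|---|---|---|
| 1 | 4.9% | 12.9% |
| 2 | 10.3% | 25.7% |

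In the same model with p=0.333 in the others, the chance of passing is P(X ≥ 19−m): 2.4% for m=0, 3.8% for m=1 and 5.8% for m=2. At p=0.207, the observed historical rate (12/58), it is below 0.04% in each case.

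**Unassessed treated patients.** Take 38 assessed patients and count u further treated patients as non-responders. The planned 10% allowance corresponds to 42−38=4.

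| Responders | u=0 (n=38) | u=2 (n=40) | u=4 (n=42) |
|---|---|---|---|
| 19 | p=0.0244 | p=0.0437 | p=0.0720 |
| 20 | p=0.0108 | p=0.0212 | p=0.0380 |
| 21 | p=0.0043 | p=0.0094 | p=0.0185 |

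The verdict changes at 19 responders with u=2, and at 19 or 20 with u=4.

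**The case against.** The strongest reply is that SAP 3.2 is explicit. It names the primary criterion and makes withdrawal for lack of efficacy non-response without any condition; the words about a missing score belong to the next sentence. On that reading only a cross-reference and a line in 4.10.1 are missing. This largely stands, and it is why 3.2 is the better reading. It does not cure 4.6.1, which describes the primary analysis without the exception.

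Protocol 5.4 also makes the disputed patient rare, and the 1 or 2 patients in the illustration have no anchor in the documents. Both points stand.

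A reader might infer that the planned test has a type I error of 3.8% or 5.8%. The documents do not support that. Those figures are the chance of passing if a stricter definition of response is assumed to be the true one. Under the definition in 4.6.1, the expected rate in that model is (1+37×0.333)/38=35.1% or (2+36×0.333)/38=36.8%, already above the null.

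A reader might also infer that the pre-intake replacement after a forbidden treatment is an error that favours the drug. It is not an error. It follows from the censoring in protocol 12.9.1.1, it discards gains made after intake, and the listed treatments need not be given for CIDP.

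Nor would the report be silent on these patients. The secondary endpoint on change in CIDP treatment counts certain added treatments against the patient, and assessments after a forbidden treatment are flagged in the listings. Neither is a responder analysis.

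Finally, adjusted INCAT is scheduled before every course from Week 3, so having no post-dose score requires an early exit without an EOS visit. Four of 42 uses the whole planned allowance. That stands. The case is still possible, because protocol 5.4 makes the EOS visit voluntary after consent is withdrawn.

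**Conclusion.** The inconsistency is real and narrow. SAP 3.2 should be taken to govern, and 4.6.1 should be brought into line with it. The two rules give different counts only for a patient withdrawn for insufficient response who is still at least 1 point better than baseline. They give different verdicts only at the boundary, between 19 and 18 of 38. How often this would happen cannot be worked out from the documents.

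The gap in the sensitivity analysis is separate. The PPS cannot show the effect of treated patients who are not in the FAS. With 4 such patients a pass at 20/38 becomes a fail at 20/42; with 2, 20/40 still passes. This assumes that the FAS omits patients with no post-dose score and that a missing outcome is counted as failure.

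There is also a minor wording point. Protocol 7.2 bars any introduction of systemic corticosteroids, while SAP 4.6 and protocol 12.9.2.2 can be read as covering an introduction only above 10 mg daily. SAP 4.6 also places a pre-screening item among treatments not allowed during the study.

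Severity is minor to should-fix.

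**What to change.** 1. In SAP 4.6.1, state that withdrawal for insufficient response is non-response whatever the observed or carried-forward score, and that this takes precedence over LOCF and over the pre-intake replacement. Cross-refer to 3.2 and list it in 4.10.1 as a change from protocol 12.9.1.3.
2. Keep the FAS primary analysis and add two supportive responder tables on the TTS. The first counts treated patients with no post-baseline score as non-responders and leaves LOCF otherwise unchanged. The second, shown separately, also counts patients with a forbidden treatment before EOS as non-responders. Separate tables show which group drives any difference, and patients with usable scores keep them in the first.
3. Reconcile the forbidden-treatment wording in SAP 4.6, protocol 7.2 and protocol 12.9.2.2. This review does not say which wording is right.

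The cost is SAP text, one line in 4.10.1 and two tables, with no new data. The supportive rates may be slightly lower. If 4 of 42 are unassessed and the true rate in the other 38 is 60%, the first table reaches p≤0.025 (21 of 42) with probability P(Bin(38, 0.60) ≥ 21) = 77.8%, against 92.2% for the primary test. The SAP should say that these tables are supportive and not a second hurdle.
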